- A pilot clinical trial with Bactek® has recently evaluated the effect of its daily administration via the sublingual route, for a total of six months, in the prevention of recurrent infections of the upper and lower respiratory tract (RRTIs) in a cohort of adult subjects. This trial was carried out with a group of subjects with RRTIs (N = 17) to assess whether sublingual immunization with a polyvalent bacterial vaccine might cause an immunomodulatory effect on the antigen-specific immune response and has a clinical impact. An immunological assessment was performed both before and at the end of the immunization. These immunological determinations included: proliferation of antigen-specific CD3+CD4+ and CD3+CD8+ T cells against Bactek® antigens, serum immunoglobulin levels, specific antibodies against the pneumococcal

polysaccharide and the tetanus toxoid, and lymphocyte subpopulations of B, T, and NK cells. It has recently been published in the journal *Clinical Experimental Immunology* under the title: "Sublingual therapeutic immunization with a polyvalent bacterial preparation in patients with recurrent respiratory infections: immunomodulatory effect on antigen-specific CD4+ T cells and clinical impact".

During the twelve-month period elapsed since the start of the therapeutic immunization, an impact on clinical control was observed in the form of a significant decrease in the incidence of upper and lower respiratory tract infections compared with the number of RRTIs that the same subjects had experienced within the twelve months preceding the start of this treatment. This cohort of subjects exhibited a decrease in the frequency of episodes of RRTIs while receiving treatment with Bactek and during the follow-up period compared with the year preceding the start of the immunization. These clinical data are consistent with observations from another placebo-controlled study evaluating the bacterial vaccine in children, which showed that its clinical response is more effective in selected subjects who experienced a greater number of RRTIs in the year preceding the start of this therapy.

[name]  
Traductor-Intérprete Jurado de INGLÉS  
Nº 9971

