**10.3. Significance Level to be Used**

The significance level for the efficacy assessment will be 0.05 for a type I error ( $\alpha$ ) and 0.2 for a type II error ( $\beta$ ).

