5.2.1. Subject Inclusion Criteria

A COPD exacerbation will be considered to be recurrent when it occurs at a frequency of at least three episodes in one year.

In this study we will include subjects who meet the following criteria:

- ★ Subjects who have provided their written informed consent.
- ★ Subjects of both sexes.
- ★ Subjects aged between 35 and 85 years.
- ★ Subjects who are capable of complying with the dosing regimen.
- ★ Subjects with a diagnosis of moderate or severe COPD according to the GOLD criteria.
 - Subjects with a predicted post-bronchodilator force expiratory volume in the first second (FEV₁) <50% (50% - 30%), with or without chronic symptoms (e.g., coughing or sputum production).
- ★ Subjects who have experienced at least three moderate exacerbations (i.e., those requiring treatment with antibiotics, systemic corticosteroids, or both, as prescribed by their general practitioner or pulmonologist in the standard consultation and/or the Emergency Department of their Clinic) or two exacerbations with at least one requiring hospitalization due to a COPD exacerbation and the other one a moderate exacerbation occurred within the last year.
- ★ Subjects who have not changed their medication for the maintenance treatment of COPD within the past 6 months.
- ★ Subjects with an accumulated consumption of ten or more pack-years. The subjects may or may not be active smokers.
- ★ Subjects included in the trial may have been vaccinated with pneumococcal polysaccharide vaccine at least 4 weeks before starting the administration of Bactek®.
- ★ Women of childbearing age must use an approved method of contraception (oral, vaginal, transdermal, intrauterine device [IUD], etc. or barrier methods) and obtain a negative result in the urine pregnancy test performed during the screening visit.

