6.1.1. Primary outcome

The primary efficacy outcome is a decrease in the mean number of COPD exacerbations. A clinical diagnosis of an exacerbation according to the GOLD definition will be considered; that is, an event occurring throughout the natural course of the disease, characterized by a change of acute onset, beyond the daily variability, in the patient's dyspnea, cough, and/or expectoration, which may require a change in the patient's usual medication.

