7.1.1. Sample Size and Power

The calculation of the sample size is based on the efficacy measured based on the decrease in the number of episodes of COPD exacerbations during the 12-month treatment period of the trial per subject.

The ratio of subjects to be distributed among the active treatment and placebo groups will be 1:1.

We estimate that subjects from group I (active treatment with the bacterial vaccine) will achieve a 60% decrease in their number of COPD exacerbations compared with a 30% decrease among those of group II (placebo). With an alpha error of 0.05 and a beta error of 0.2, and assuming a dropout rate of 20-25%, the number of subjects to be recruited would be 90 per study group, with an overall total of 180 trial subjects.

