7.1.7. Adjustments for Covariates

This study will use the draft guidance Adjusting for Covariates in Randomized Clinical Trials for Drugs and Biological Products - Guidance for Industry (CDER, May 2021, Revision 1). All baseline characteristics will be used to study exacerbations appearance in time using a Poisson regression or equivalent (see below).

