7.1.9. Model Assumptions

Primary endpoint analysis will use a median test or a Mann-Whitney test. Secondary endpoints will use relevant tests (Fisher's exact, T test, etc.) and a Poisson regression for exacerbations with baseline characteristics as covariates.

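### The SAP does not say which primary analysis decides, and none of its sections names the prior-year exacerbation count as a covariate; if the unadjusted rank or median test decides, precision is given up

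*SAP*

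**What the plan says.** **Test assigned to the primary endpoint.** SAP 6.1.1: "The primary efficacy outcome is a decrease in the mean number of COPD exacerbations". SAP 7.1.9: "Primary endpoint analysis will use a median test or a Mann-Whitney test". Neither test takes a covariate. The next sentence of 7.1.9 puts the Poisson regression with baseline covariates among the tools for secondary endpoints. Protocol 10.1 likewise gives the number of exacerbations a t test or Mood's median test, both unadjusted.

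**Primary Efficacy Analysis, SAP 7.4.1.** This section lists chi-square or Fisher's exact test, relative risks with median or Mann-Whitney tests, a Cox model, and a Poisson model with robust estimation that is there to bring in covariates. It offers Stata's exposure option if observation times differ. No method is marked as decisive.

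**Covariates, SAP 7.1.7.** "All baseline characteristics will be used to study exacerbations appearance in time using a Poisson regression or equivalent". The characteristics are not listed.

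**The prior-year count.** SAP 5.2.1 and Protocol 6.1 admit "Subjects who have experienced at least three moderate exacerbations" in the last year, or two exacerbations of which at least one led to hospitalisation. The count must therefore be established for everyone enrolled. No section names it as a covariate, and Table 1 (Protocol 5.2.1, SAP 4.1) has no separate row for it.

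**The concern.** Patients who exacerbated often last year tend to do so again. An unadjusted test leaves those stable differences between patients in the error of the treatment comparison, whereas adjusting for the prior-year count removes part of them. The adjustment does not need the entry and on-trial definitions of an exacerbation to match. Any pre-randomisation measure correlated with the outcome can serve.

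Two things are at stake. One is precision in the primary comparison. The other is clarity: 7.1.9 and 7.4.1 support different readings of which result is primary, one unadjusted and one adjusted. Randomisation is in blocks of 6 with no stratification described (SAP 7.1.4), so the design itself does not balance prior-year counts.

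**Working it through.** **1. The plan's own figure.** Protocol 10.3: "The significance level for the efficacy assessment will be 0.05 for a type I error". SAP 7.1.1 sets beta at 0.2, dropout at 20-25%, a 60% versus 30% decrease, and 90 per group. Sidedness is not stated; two-sided is assumed here.

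Read as two proportions:

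n = [1.960·√(2·0.45·0.55) + 0.842·√(0.6·0.4 + 0.3·0.7)]² / 0.30² = (1.379 + 0.565)² / 0.09 ≈ 42 per group

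After dropout this is 42/0.80 = 53 to 42/0.75 = 56. With continuity correction it is 49, or 62 to 66 after dropout. Neither gives 90. Read as a mean or a rate, the figure cannot be checked, because no SD, placebo rate or dispersion is stated. So 80% is used below as the design target, not as a verified power.

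**2. Normal-theory gain from a baseline covariate.** Adjustment multiplies the residual variance by 1 − ρ². Starting from 80%:

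power = Φ[(1.960 + 0.842)/√(1 − ρ²) − 1.960]

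| ρ (assumed) | 1 − ρ² | 2.802/√(1 − ρ²) | Power | Gain, points |
|---|---|---|---|---|
| 0.2 | 0.96 | 2.860 | 81.6% | 1.6 |
| 0.3 | 0.91 | 2.937 | 83.6% | 3.6 |
| 0.4 | 0.84 | 3.057 | 86.4% | 6.4 |
| 0.5 | 0.75 | 3.235 | 89.9% | 9.9 |
| 0.6 | 0.64 | 3.502 | 93.8% | 13.8 |

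If the starting point is instead the proportions reading with 68 to 72 evaluable per group, power is already 94.9% to 95.9%. At ρ = 0.5 it becomes 98.6% to 99.0%, a gain of 3 to 4 points.

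**3. Simulation with counts.** The formula in step 2 is for a linear model, so counts were also simulated. Set-up: 70 evaluable per arm (90 less 20-25% is 67.5 to 72), gamma-distributed patient rates that stay the same from year to year, entry limited to 3 or more prior events, placebo at 70% of the prior rate, two-sided 5%, 800 trials per scenario. Means, dispersions and the weaker rate ratios are assumptions. The planned rate ratio is (1 − 0.60)/(1 − 0.30) = 0.57.

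| Mean, dispersion, rate ratio | Mann-Whitney | Poisson, no covariate | Poisson + log prior count | From changing test | From covariate alone |
|---|---|---|---|---|---|
| 2.5, 1, 0.68 | 70.8% | 77.2% | 88.2% | 6.4 | 11.0 |
| 3.5, 0.5, 0.72 | 64.8% | 70.2% | 79.2% | 5.4 | 9.0 |
| 1.5, 1, 0.68 | 64.8% | 71.8% | 78.2% | 7.0 | 6.4 |
| 3.5, 1, 0.65 | 78.6% | 84.6% | 97.4% | 6.0 | 12.8 |
| 2.5, 0.5, 0.57 | 94.5% | 96.5% | 98.4% | 2.0 | 1.9 |
| 2.5, 1, 0.57 | 93.4% | 95.9% | 99.0% | 2.5 | 3.1 |

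Correlations were 0.38 to 0.65 despite the entry cut-off. Type I error of the adjusted model was 5.4%. Near 97% power the standard error of one entry is about √(0.97·0.03/800) = 0.6 points, so the last two rows support no more than a gain of a few points.

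**4. Drift in patient rates.** Year-to-year gamma variation lowers the correlation. With variance 0.2 to 0.3, ρ was 0.40 to 0.43 and adjustment alone still added about 10 points, from a base of 55% to 57%. In separate runs with variance 0.3 to 0.6, ρ was 0.26 to 0.42 and adjustment alone added about 2 to 8 points.

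**The case against.** A reader might infer that the primary analysis has no covariate adjustment. The documents do not support that. SAP 7.4.1 includes a covariate-adjusted Poisson model under the primary heading, and 7.1.7 commits to using the baseline characteristics. A count needed for entry would ordinarily be one of them, and Table 1 records inclusion criteria, medical history and healthcare resource use at baseline. What remains is that the count is not named and that the sentence assigning a primary test assigns an unadjusted one.

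A reader might also infer that the plan loses a fixed 10 points of power. That needs ρ = 0.5, which the documents do not give, and a base of 80%, which the stated inputs do not reproduce. The larger differences between the Mann-Whitney and adjusted Poisson columns also mix a change of test with the covariate, and they arise at effects weaker than planned.

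Further points that stand:

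- Chance imbalance is not ignored. Protocol 10.1 compares baseline variables and adjusts if confounding is found. Adjustment triggered by the data is weaker than a pre-specified covariate, but it is a provision.
- If the endpoint is a per-patient decrease, a rank test on the change already uses the prior count. It does so inefficiently: at ρ = 0.5 the change has variance 2(1 − 0.5) = 1 against 0.75 after adjustment, so 80% again becomes 89.9%.
- The Protocol 3.4.2 remark that response was "more effective in selected subjects who experienced a greater number of RRTIs in the year preceding the start of this therapy" concerns children with respiratory infections and a difference in treatment response. It is not evidence of prognostic correlation in COPD.
- The simulation uses one event definition and omits the two-exacerbation entry route.

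**Conclusion.** The point holds in a conditional form. SAP 7.1.9 and 7.4.1 do not agree on what decides the primary comparison, and the most obvious prognostic covariate is not named anywhere. If the unadjusted test decides, precision is lost. From an assumed 80% base the gain available by normal theory is about 4 points at ρ = 0.3, 6 at 0.4 and 10 at 0.5. At the full planned effect the covariate alone is worth about 2 to 3 points in simulation. It is worth more (6 to 13 points) only if the true effect is weaker, at rate ratios of 0.65 to 0.72 with stable patient rates. All of this rests on assumed correlations, rates and dispersion. If the covariate Poisson model in 7.4.1 decides and the prior-year count is among its covariates, this loss does not arise. The documents do not show that the planned comparison is biased. The change is worth making because it is cheap and it settles which analysis is primary.

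**What to change.** In SAP 7.1.9 and 7.4.1, name one primary analysis: the robust Poisson model already in 7.4.1, with the exposure option for follow-up time. Make log(exacerbations in the year before entry) a named, mandatory covariate, entered as a baseline variable from the eligibility record. Both entry routes require at least two events, so the log is always defined. Keep the unadjusted rank test as a sensitivity analysis and label the other tests in 7.4.1 as supportive. Using the same covariate in the Cox model is optional, because it changes the hazard ratio being estimated.

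The cost is SAP wording, settled before unblinding, and one numeric field. The primary summary also changes from a rank comparison to an adjusted rate ratio, which should be stated openly. Error in the prior-year count, which relies on records or recall, reduces the gain but does not bias the comparison.

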7.2. Subject Disposition

A table of subject disposition by treatment group displaying number and percent of subjects included in the FAS, in the PP analysis set and in the safety analysis set as well as number and percent of subjects enrolled and subjects withdrawn will be presented.

7.3. Demographic and Baseline Characteristics

Demographic and other baseline characteristics will be summarized displaying number of subjects, mean, standard deviation, median, 25 and 75-percentiles, minimum and maximum for continuous variables and frequency tables for categorical variables.

7.4. Efficacy Evaluation

The efficacy analyses will be conducted based on all the analysis sets.

7.4.1. Primary Efficacy Analysis

The rate of exacerbations per patient and the severity of these exacerbations will be compared using the chi-square test or Fisher's exact test. The relative risks will be estimated together with their 95% CI and median or Mann-Whitney tests. The number needed to treat (NNT) or number of events prevented per treatment will be estimated.

The rate of episodes occurred over time will be calculated, and the hazards ratio (HR) will be estimated together with its 95% CI following a Cox proportional-hazards model. The NNT (number of patients that need to be treated to avoid an event) will also be estimated.

Poisson model with robust estimation of incidence density will be used to include covariates in the model.

Poisson model assumes that the response variable is a count variable (number of exacerbations) and each subject has the same length of observation time. If the observation time for subjects varied, the Poisson model would need to be adjusted to account for the varying length of observation time per subject. In this case a Stata exposure option, *exposure(varname)*, will be used where *varname* corresponds to the length of time an individual was followed to adjust the Poisson regression estimates. Also, Poisson model assumes that the dependent variable is not over-dispersed and does not have an excessive number of zeros (in whose case Negative Binomial and Zero-inflated models would be preferred).

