7.1. General Considerations

Descriptive statistics will be provided for selected demographic, safety, and exacerbations by dose, dose schedule, and time as appropriate. Descriptive statistics on continuous data will include means, medians, standard deviations (and standard errors for post-baseline data), quartiles, and ranges, while categorical data will be summarized using frequency counts and percentages. Graphical summaries of the data may also be presented.

When data are summarized by time, the values recorded against the scheduled time points listed in the protocol will be used. When assessing minimum/maximum increases or decreases over the study, all assessments, including unscheduled assessments will be used. Data listings will include all available data from all enrolled subjects unless specified otherwise.

This analysis does not use significance levels. Exact, two-sided 95% confidence intervals were used for the Histamine equivalent concentration.

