7.1.2. Handling of Missing Data

No imputation of data will be carried out in case of missing data, but all available data will be used to its full extent.

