7.1.5. Multiple Comparison

If multiple comparisons are needed, Holm adjustment for multiple comparisons will be used. However, the analysis will try to obviate multiple comparisons except as exploratory analysis.

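### The SAP fixes no single primary analysis of the exacerbation count: the test, analysis set and time window are left open, and the 0.05 level is contradicted

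*SAP*

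**What the plan says.** **Test.** SAP 7.1.9: "Primary endpoint analysis will use a median test or a Mann-Whitney test". The same paragraph places Poisson regression with the secondary endpoints. SAP 7.4.1, the primary efficacy section, starts with "The rate of exacerbations per patient and the severity of these exacerbations will be compared using the chi-square test" or Fisher's exact test. It goes on to relative risks with median or Mann-Whitney tests, a Cox hazard ratio and a robust Poisson model. Negative binomial or zero-inflated models take over if the Poisson assumptions fail, with no decision rule. SAP 7.4.2 tests the number of exacerbations again, by t test or Mood's median test.

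**Set.** SAP 7.4: "The efficacy analyses will be conducted based on all the analysis sets". Protocol 10.1 uses both ITT and per-protocol. SAP 5.1.2 and Protocol 10.1 define ITT by at least one dose, Protocol 10.7 adds a week 25 assessment, and SAP section 8 describes a full analysis set of everyone enrolled as a secondary analysis.

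**Window.** The primary outcome in SAP 6.1.1 has none. Sizing in SAP 7.1.1 uses the 12-month treatment period, SAP 6.1.2 lists the 12-month rate as secondary, and SAP 7.4.2 looks at 3, 6 and 12 months and the whole study.

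**Level.** Protocol 10.3: "The significance level for the efficacy assessment will be 0.05 for a type I error". SAP 7.1.1 also uses 0.05. SAP 7.1: "This analysis does not use significance levels". The next sentence there concerns a histamine measure that is no endpoint of this trial.

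**Multiplicity and missing data.** SAP 7.1.5: "If multiple comparisons are needed, Holm adjustment for multiple comparisons will be used". No family is defined. SAP 7.1.2: "No imputation of data will be carried out in case of missing data". Protocol 10.5 prescribes last observation carried forward.

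**The concern.** A confirmatory primary analysis needs one estimate, one population, one period and one threshold fixed before the data are seen. Here each is open or contradicted. If the reported primary result may be picked from several unadjusted tests and sets, the 0.05 level no longer bounds the false-positive rate. The 80% power claim cannot be attached to any analysis, because the listed tests differ widely in sensitivity.

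The only tests SAP 7.1.9 names for the primary endpoint also work on raw counts and ignore how long each patient was observed. Yet the trial is sized "With an alpha error of 0.05 and a beta error of 0.2, and assuming a dropout rate of 20-25" percent, Protocol 6.3.4 does not follow voluntary dropouts, and the SAP imputes nothing. A patient lost at month 2 has fewer exacerbations simply through leaving, so unequal dropout would favour the arm that loses more patients.

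**Working it through.** **1. The stated sample size.** The documents give 60% versus 30% decrease, alpha 0.05, beta 0.2, dropout 20-25% and 90 per group. They give no test, baseline rate, SD or dispersion. Reading 60% and 30% as two proportions:

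n = [1.96·√(2·0.45·0.55) + 0.8416·√(0.6·0.4 + 0.3·0.7)]² / 0.3² = (1.379 + 0.565)² / 0.09 ≈ 42 per arm.

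Dividing by 0.80 and 0.75 gives 53 and 56 (62 and 66 with continuity correction), not 90.

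Reading them as falls from an assumed 3 exacerbations a year gives rates 3 × 0.7 = 2.1 and 3 × 0.4 = 1.2. With negative-binomial dispersion k:

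n = (1.96 + 0.8416)² · (1/2.1 + 1/1.2 + 2k) / [ln(1.2/2.1)]² = 7.849 · (1.3095 + 2k) / 0.3132.

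- k = 0.5: 58 per arm, or 73-78 after dropout.
- k = 1.0: 83 per arm, or 104-111 after dropout.

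Over baselines of 2-4 a year and k of 0-2 the range after dropout is 32 to 200. So 90 is not shown to be wrong, but it cannot be tied to any listed test.

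**2. Simulation set-up.** Assumptions not in the documents: gamma-Poisson counts, 90 per arm, 22.5% dropout uniform over 12 months, per-protocol taken as completers. There were 8,000 trials per scenario. Monte Carlo standard error is about 0.25 points for error rates and at most 0.6 points for power. Chi-square is read as any-versus-none and Cox as time to first event (log-rank), because SAP 7.4.1 does not say.

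**3. Power at 2.1 versus 1.2 a year.**

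| Test | k = 0.5 | k = 1.0 |
|---|---|---|
| Robust Poisson with exposure | 92% | 80% |
| Mann-Whitney | 82% | 65% |
| Median | 73% | 56% |
| Cox, first event | 68% | 52% |
| Chi-square, any versus none | 54% | 41% |

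With a baseline of 2 a year, the exposure model has 84% and 73%, and Mann-Whitney 74% and 59%.

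**4. No effect (2.1 a year in both arms), equal dropout.** Each single test rejects 4.5-5.6% of the time. The chance of at least one p<0.05 is:

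- median or Mann-Whitney: 7%;
- any of the five tests, full analysis set: 13%;
- the same five in full analysis set plus per-protocol: 18%.

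A second simulation with 1,500 null trials gave 6% for the median/Mann-Whitney pair. Across six tests (t test added, Fisher for chi-square), two sets and two windows (12 and 18 months) it gave 20-24%.

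**5. Holm over the five tests.** The error falls to 3%. The chance that any test passes is 83% and 65% at the two dispersions, below the exposure model alone at 92% and 80%.

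**6. No effect, unequal dropout.** With uniform dropout times, mean follow-up is 1 − d/2 years. At 15% versus 30% that is 0.925 and 0.85, so expected counts at 2.1 a year are 1.94 and 1.79, an apparent fall of about 8% with no effect. Mann-Whitney then rejects 8-9% of the time, the exposure model 5-6% and Cox 5%. At 20% versus 25% all tests stay at 5-6%.

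**The case against.** The strongest reply is that the intent can be recovered:

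- SAP 7.4.1 also names median or Mann-Whitney tests, so it overlaps with 7.1.9. Poisson enters 7.4.1 to bring in covariates, which suits an adjusted companion to an unadjusted test. Rate and severity are secondary outcomes in SAP 6.1.2, so the chi-square sentence may be misplaced secondary text.
- Twelve months is implied by the sizing paragraph and by the 50-week efficacy period in the per-protocol definition.
- The significance-level sentence sits beside an unrelated histamine sentence and looks like leftover text.
- SAP 7.1.5 also says multiple comparisons will be avoided except as exploratory work, so 7%, the cost of the either/or in 7.1.9 alone, is a fairer headline than 13% or 18%.
- Unequal dropout matters only in a hypothetical 15% versus 30% case.

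Much of this is fair. The 13% and 18% assume free choice without Holm. The dropout effect is negligible at 20% versus 25%. The median-test power depends on how ties are split: counting values above the median gave 73% and 58% in a further check, and values at or above it 56% and 40%. The simulations also ignore the replacement rule in Protocol 6.3.3.

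None of it names a primary test, set or window. Even the most generous reading leaves two tests joined by "or", and Poisson secondary in one section and under the primary heading in another. The reader must infer what a SAP exists to state.

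**Conclusion.** The concern holds and must be fixed. The contradictions are in the text and depend on no assumption. Their size does depend on the assumed rates, dispersion and dropout pattern. If only the choice in 7.1.9 is open, the false-positive chance is about 7%; it is 13% across the five tests and 18% with the per-protocol set added. Power for the same trial ranges from 92% to 54% at dispersion 0.5 and from 80% to 41% at 1.0, depending on the test. Each test alone is close to 5% when dropout is equal, and the stated 80% power is not refuted. The fault is that neither figure belongs to a specified analysis. Ignoring follow-up time is a lesser matter unless dropout differs clearly between arms, but the model that accounts for it is also the most powerful of the five.

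**What to change.** In SAP 7.1.9 and 7.4.1 state one primary analysis, in the same words:

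- **Endpoint and window:** number of exacerbations over the 12-month treatment period. Put the window into SAP 6.1.1 too.
- **Set:** the SAP 5.1.2 full analysis set, all randomized with at least one dose. Reconcile Protocol 10.7 (week 25 assessment) and SAP section 8 (all enrolled) with it.
- **Model:** one rate model fixed in advance, for example robust-variance Poisson with log follow-up time as offset. Negative binomial is acceptable if chosen now rather than after seeing the data. List the covariates, if any.
- **Result:** rate ratio with 95% CI, tested at two-sided 0.05. Protocol 10.3 does not give the sidedness.

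Label chi-square/Fisher, median, Mann-Whitney, t test, Cox, per-protocol and 18-month results as supportive. Delete the significance-level and histamine sentences from SAP 7.1. Reconcile SAP 7.1.2 with the carry-forward rule in Protocol 10.5. Restate power for the named model with its baseline rate and dispersion.

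The cost is mostly SAP wording: the exposure model is already in 7.4.1 and needs only each patient's follow-up time. It must be done before database lock. The documents do not show whether lock has occurred; if it has, the choice should be reported as made afterwards.

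### SAP 7.4.1 and protocol 10.1 assign chi-square or Fisher's exact test, a relative risk and an NNT to a per-patient rate of a repeatable event, without defining the table or ranking the test against the other listed methods

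*SAP*

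**What the plan says.** SAP 6.1.1 defines the outcome on the count scale: "The primary efficacy outcome is a decrease in the mean number of COPD exacerbations". SAP 7.4.1, headed Primary Efficacy Analysis, opens with "The rate of exacerbations per patient and the severity of these exacerbations will be compared using the chi-square test" or Fisher's exact test. It attaches relative risks with 95% confidence intervals and adds "The number needed to treat (NNT) or number of events prevented per treatment will be estimated". Protocol 10.1 carries the same test and the same effect measures.

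The same SAP section also lists:
- median or Mann-Whitney tests;
- a Cox model with a hazard ratio and a further NNT;
- a count model: "Poisson model with robust estimation of incidence density will be used to include covariates in the model". An exposure term is to be used if follow-up varies. If the counts are over-dispersed or zero-heavy, other models are named: "in whose case Negative Binomial and Zero-inflated models would be preferred".

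SAP 7.1.9 states: "Primary endpoint analysis will use a median test or a Mann-Whitney test". It places Fisher's exact test among the tests for secondary endpoints. Neither document ranks these methods.

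**The concern.** Chi-square and Fisher's test compare proportions, and a relative risk and an NNT describe a two-category outcome. A rate of exacerbations per patient is neither. To apply these tests someone must first build a table, and the plan does not say whether its entries are patients or episodes.

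The choice matters. Counting patients with any exacerbation discards most of the information in the count. Entry requires frequent exacerbators ("Subjects who have experienced at least three moderate exacerbations" in the past year, or two with one hospitalised), so many patients in both arms can be expected to have at least one. Counting episodes ignores that episodes in one patient are related. The reported NNT also depends on which quantity is meant, and the text leaves that open.

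**Working it through.** **The plan's own figure.** The documents give no power for this comparison. The nearest figure is 90 per group, from a 60% versus 30% decrease with alpha 0.05, beta 0.2 and 20-25% dropout. Read as two proportions (two-sided), those inputs give 42 per arm, or 42/0.80 = 53 to 42/0.75 = 56 after dropout, so 90 is not reproduced. That is a separate matter and does not decide this point.

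**Inputs.**
- From the documents: 60% versus 30% decrease, 90 per arm, 20-25% dropout, 12 months (SAP 7.1.1).
- Assumed: a baseline of 3 exacerbations a year, suggested by the entry criterion. The means are then 3 × 0.70 = 2.1 (placebo) and 3 × 0.40 = 1.2 (active), a rate ratio of 1.2/2.1 = 0.57.
- Assumed: negative binomial counts with dispersion k, where k=0 is Poisson; a two-sided test; 22.5% dropout with partial follow-up counted.

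**Reading 1: any versus none per patient.** P(any) = 1 − (1 + kμ)^(−1/k), or 1 − e^(−μ) at k=0. Over a full year:
- k=0: 0.878 versus 0.699, relative risk 0.80;
- k=1: 0.677 versus 0.545, relative risk 0.81.

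A rate ratio of 0.57 therefore appears as a relative risk of about 0.80. Simulated power with 90 per arm (repeat runs moved these by up to about three percentage points):

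| k | Fisher, any/none | Robust Poisson |
|---|---|---|
| 0 | 71% | 99% |
| 0.4 | 52% | 94% |
| 1 | 36% | 80% |

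**Reading 2: episodes pooled as independent.** The true variance of a count is 1 + kμ times the Poisson variance. At μ=2.1 this is 1 + 0.4 × 2.1 = 1.84 and 1 + 1 × 2.1 = 3.10. The actual two-sided type I error is about 2[1 − Φ(1.96/√(1 + kμ))]:
- k=0: 5%;
- k=0.4: 1.96/1.356 = 1.445, giving 15%;
- k=1: 1.96/1.761 = 1.113, giving 27%.

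Simulation with partial follow-up gives about 15% and 25%. Robust Poisson stays at about 5-6%.

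**Reading 3: patients by number of exacerbations (0, 1, 2, 3, 4+).** With 68 completers per arm (90 less 25%), type I error holds at 4-5%. Power compares as follows:

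| k | Chi-square, any/none | Chi-square, 2×5 table | Rate analysis |
|---|---|---|---|
| 0 | 73% | 90% | 98% |
| 0.5 | 48% | 61% | 86% |
| 1 | 35% | 43% | 72% |

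This reading yields no single relative risk or NNT.

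**Sensitivity to the baseline rate.** With 68 per arm and baselines of 2 to 4 a year, any/none power divided by rate-analysis power is 0.69-0.77 at k=0, 0.50-0.64 at k=0.5 and 0.43-0.57 at k=1.

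**NNT versus events prevented.** The NNT for at least one event by 12 months is 1/(0.878 − 0.699) = 5.6 at k=0 and 1/(0.677 − 0.545) = 7.6 at k=1. Events prevented are 2.1 − 1.2 = 0.9 per patient-year, or one per 1/0.9 = 1.11 patient-years. The ratio is 5.6/1.11 = 5.0 to 7.6/1.11 = 6.8.

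**The case against.** The strongest reply is that chi-square is not the trial's primary test. SAP 7.1.9 gives the primary endpoint a median or Mann-Whitney test and puts Fisher's test with the secondary endpoints. Protocol 8.1 lists the number of exacerbations as primary and the rate per patient as secondary, and protocol 10.1 tests the number by Student's t or Mood's median test. A suitable count model is already in SAP 7.4.1. This stands, and it rules out reading the plan as resting on chi-square alone. It does not settle the matter: 7.4.1 places the sentence first under the primary heading, 7.1.9 disagrees with it, Poisson is brought in only to include covariates, and nothing says which result decides.

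A reader might also infer that the plan halves power or inflates false positives. The documents support neither as a fixed result:
- The power loss depends on a dispersion they do not state; with none, power falls by a little over a quarter.
- Episode pooling is nowhere planned. The terms relative risk, NNT and per patient suggest patient-level proportions, and SAP 7.4.2 separately studies the appearance of any exacerbation at set times. Without over-dispersion, pooling would not inflate type I error anyway.
- Those two readings are not exhaustive, since a patients-by-count table is a third.

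The Cox paragraph of 7.4.1 does gloss NNT as patients treated per event avoided. It gives no time horizon and does not say whether first or all events count.

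**Conclusion.** The concern holds in a limited form. The stated test and effect measures do not fit the stated outcome, the table is undefined, and SAP 7.1.9 and 7.4.1 conflict with no ranking of methods. Under the assumed rates and dropout, the any/none reading loses 28 percentage points of power with no over-dispersion (99% to 71%) and 42-44 points at k=0.4-1. Episode pooling, if anyone did it, would carry a type I error of about 15-25% at k=0.4-1. The 5-fold gap between the two quantities offered as alternatives is present even without over-dispersion. All sizes rest on an assumed baseline of 3 a year and assumed dispersion. The mismatch between test and outcome rests on neither.

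**What to change.** In SAP 7.4.1 and protocol 10.1:
1. Remove chi-square, Fisher's test and the relative risk for the exacerbation rate, or confine them to a defined secondary endpoint of at least one exacerbation by month 12.
2. Name the count model already in SAP 7.4.1 (robust Poisson or negative binomial, chosen in advance, with follow-up time as exposure) as the analysis of the number of exacerbations. Report the rate ratio and rate difference with 95% confidence intervals.
3. Reconcile SAP 7.1.9 with that choice and state the role of the median, Mann-Whitney and Cox analyses. Deleting chi-square alone would leave those unranked.
4. If an NNT is kept, define it only for at least one exacerbation by a stated time, and report events prevented per patient-year separately.

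The cost is wording in two documents. The downside is one 2×2 table dropped or relabelled and a less striking NNT.
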